6.1.2 Guidelines for continuation of treatment

For guidelines for continuation of treatment, refer to [Section 6.3](#) Dosing modifications.

Patients who permanently discontinue one of the study drugs for any reason other than disease progression may continue the other study drug as part of the trial therapy at the investigators discretion until disease progression, unacceptable toxicity, death or discontinuation from study treatment due to any other reason and should follow the protocol safety and efficacy assessments as scheduled. After discontinuing all study treatment, further treatment is left to the physician's discretion.

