6.3.1.2 Alpelisib/placebo

Management of severe or intolerable adverse reactions requires dose reduction, temporary interruption, and/or discontinuation of alpelisib therapy. A maximum of 2 dose reductions will be allowed, after which the patient will be discontinued from treatment with alpelisib/placebo. Dose reduction should be based on the worst preceding toxicity.

Please refer to [Table 6-2](#) and [Table 6-3](#) for guidance.

Table 6-2 Dose reduction sequential steps for alpelisib/placebo

Alpelisib/placebo dose level	Dose and schedule	Number of tablets & strength
Starting dose	300 mg/day continuously	1 x 200 mg tablet and 2 x 50 mg tablet
Dose level -1	250 mg/day continuously	1 x 200 mg tablet and 1 x 50 mg tablet
Dose level -2	200 mg/day continuously	1 x 200 mg tablet

Recommendations for dose reduction or dose interruption of alpelisib/placebo in the management of adverse reactions are summarized in [Table 6-3](#). No dose modification for fulvestrant is permitted. Clinical judgment of the treating physician, including confirmation of lab values if deemed necessary, should guide the management plan of each patient based on individual benefit/risk assessment.

However, treatment must be discontinued as indicated in [Table 6-3](#).

After treatment is resumed at a lower dose:

- If the same toxicity recurs with the same severity, then the next treatment re-initiation must resume at a lower dose irrespective of duration.
- Once the alpelisib/placebo dose has been reduced, no re-escalation will occur, even upon resolution of AE.

If a patient requires a dose delay of alpelisib/placebo for > 28 days from the intended day then the patient must be discontinued from alpelisib/placebo, but may continue on fulvestrant. All scheduled assessments will continue to be performed. If fulvestrant is held for more than 35 days since a planned injection, then fulvestrant should be permanently discontinued. The patient may continue on alpelisib/placebo at the discretion of the investigator until study completion, in which case all scheduled assessments will continue to be performed.

Table 6-3 Criteria for interruption and re-initiation of alpelisib/placebo treatment

Dose Modifications for alpelisib/placebo as specified below. Fulvestrant may be continued while alpelisib/placebo dose is being held, at the investigators discretion, and as specified in Section 6.3.1	
Worst toxicity -CTCAE Grade (value)	Dose Modifications for alpelisib/placebo

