Cardiac - Left Ventricular Systolic Dysfunction	
Asymptomatic, resting ejection fraction 40-50%; or 10-20% drop from baseline	
 -Maintain dose level, and continue alpelisib with caution -Repeat LVEF within 4 weeks or as clinically appropriate
Symptomatic, responsive to intervention, ejection fraction 20-39% or > 20% drop from baseline	
 -Omit alpelisib/placebo until resolved* (as defined below), then \downarrow 1 dose level -LVEF measurement to be repeated, if not resolved* within 28 days permanently discontinue patient from alpelisib/placebo treatment
Refractory or poorly controlled, ejection fraction < 20%	Permanently discontinue patient from alpelisib/placebo
<small>*the event is considered resolved when the patient is asymptomatic, has a resting ejection fraction \geq 40% and \leq 20% decrease from baseline.</small>	

Dose Modifications for alpelisib/placebo as specified below. Fulvestrant may be continued while alpelisib/placebo dose is being held, at the investigators discretion, and as specified in Section 6.3.1	
Worst toxicity -CTCAE Grade (value)	Dose Modifications for alpelisib/placebo
Other Cardiac Events	
Grade 1 or 2	Maintain dose level
Grade 3	Omit dose until resolved to \leq Grade 1, then \downarrow 1 dose level
Grade 4	Permanently discontinue patient from alpelisib/placebo
Investigations (Gastrointestinal)	
Diarrhea (see also Appendix 4)	
Grade 1	Maintain dose level but initiate appropriate medical therapy and monitor as clinically indicated
Grade 2	Omit dose until resolved to \leq Grade 1, then restart at same dose If diarrhea returns as \geq Grade 2, then omit dose until resolved to \leq Grade 1, then decrease 1 dose level
Grade 3	Omit dose until resolved to \leq Grade 1, then \downarrow 1 dose level Manage according to local standard of care medical management, including electrolyte monitoring, administration of antiemetics and antidiarrhoeal medicinal products and/or fluid replacement and electrolyte supplements, as clinically indicated
Grade 4	Discontinue patient from treatment. Manage according to local standard of care medical management, including electrolyte monitoring, administration of antiemetics and antidiarrhoeal medicinal products and/or fluid replacement and electrolyte supplements, as clinically indicated.
Investigations (Pancreatic)	
Pancreatitis	

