Grade 2 (enzymatic elevation or radiologic findings only)	Omit dose until resolved to Grade \leq 1, then resume treatment at \downarrow 1 dose level. If toxicity recurs, permanently discontinue patient from alpelisib/placebo
Grade 3	
 For patients deriving clinical benefit upon investigator's judgement: 
 Omit dose until complete resolution of symptoms and lipase resolved to Grade \leq 1, then resume treatment at \downarrow 1 dose level. Only 1 dose reduction is allowed. 
 If recovery to \leq Grade 1 is greater than 28 days, the patient must be discontinued from the study. If toxicity reoccurs, permanently discontinue patient from alpelisib/placebo Permanently discontinue patient from alpelisib/placebo
Grade 4	Permanently discontinue patient from alpelisib/placebo
Stomatitis/Oral mucositis (see also Appendix 5)	
Grade 1/Tolerable Grade 2	Maintain dose level. Non-alcoholic or salt water mouth wash.
Intolerable Grade 2 or Grade 3	First occurrence: hold until \leq Grade 1 and \downarrow 1 dose level (if stomatitis is readily manageable with optimal management, re-introduction at the same level might be considered at the discretion of the investigator). Second occurrence: hold until \leq Grade 1 and \downarrow 1 dose level.
Grade 4	Permanently discontinue patient from alpelisib/placebo.

Dose Modifications for alpelisib/placebo as specified below. Fulvestrant may be continued while alpelisib/placebo dose is being held, at the investigators discretion, and as specified in Section 6.3.1	
Worst toxicity -CTCAE Grade (value)	Dose Modifications for alpelisib/placebo
Skin and subcutaneous tissue disorders	

Consultation with a dermatologist is highly recommended for better assessment and management of alpelisib-induced skin toxicity. (see also Section 6.3.2.1.2). Dermatologist consultation is mandated for serious cutaneous reactions (i.e. fulfilling seriousness criteria for AE Reporting) and for severe cutaneous reactions like Stevens-Johnson-Syndrome, Toxic Epidermal Necrolysis, Erythema Multiforme, Drug Reaction with Eosinophilia and Systemic Symptoms (DRESS)
	
Rash	

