7.1.3 Discontinuation of study treatment

Patients may voluntarily discontinue from alpelisib/placebo and/or fulvestrant for any reason at any time. If a patient decides to discontinue from the study treatment, the investigator must make every effort (e.g. telephone, e-mail, letter) to determine the primary reason for this decision and record this information in the patient's chart and on the appropriate CRF pages. They may be considered withdrawn if they state an intention to withdraw, fail to return for visits, or become lost to follow-up for any other reason.

The investigator should discontinue alpelisib/placebo and/or fulvestrant for a given patient if, she/he believes that continuation would be detrimental to the patient's well-being.

For patients who discontinue treatment for reasons other than documented disease progression, death, lost to follow-up, or withdrawal of consent, tumor assessments must continue to be performed every 8 weeks during the first 18 months, every 12 weeks until 36 months, then as clinically indicated until documented disease progression, death, lost to follow-up, or withdrawal of consent.

Study treatment must be discontinued under the following circumstances:

- Adverse event or laboratory abnormalities as indicated in [Section 6.3](#).
- Pregnancy
- Lost to follow-up
- Physician decision
- Subject/guardian decision
- Death
- Progressive Disease
- Study terminated by sponsor
- Technical problems
- Use of prohibited treatment and medications refer to [Section 6.4.3](#) and [Section 14.2](#).
- Any other protocol deviation that results in a significant risk to the patient's safety

The appropriate personnel from the site and Novartis will assess whether alpelisib/placebo plus fulvestrant treatment should be discontinued for any patient whose treatment code has been broken inadvertently for any reason.

Patients who discontinue only one of two medications (fulvestrant or alpelisib/placebo) should NOT be considered withdrawn from the study. They should continue taking fulvestrant only or alpelisib/placebo only (as applicable) as per investigators' clinical judgment, and return for the assessments indicated in [Table 7-1](#).

If they fail to return for these assessments for unknown reasons, every effort (e.g. telephone, email, letter) should be made to contact them as specified in [Section 7.1.8](#).

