In addition to the general withdrawal criteria, if alpelisib dosing is held for > 28 days from the intended day then alpelisib should be permanently discontinued. If fulvestrant is held for more than 35 days since a planned injection, then fulvestrant should be permanently discontinued.

Patients who completely discontinue study treatment (i.e. fulvestrant and alpelisib/placebo) should be scheduled for an End of Treatment (EOT) visit as soon as possible, and at least within 14 days after the date study treatment is permanently discontinued, at which time all of the assessments listed in [Table 7-1](#) for the EOT visit will be performed.

If the decision to withdraw the patient occurs at a regularly scheduled visit, that visit may become the EOT visit rather than having the patient return for an additional visit.

An end of phase disposition CRF page called "End of Treatment" disposition page should be completed, giving the date and primary reason for discontinuation.

At a minimum, all patients who discontinue study treatment, including those who refuse to return for a final visit, will be contacted for safety evaluations during the 30 days following the last dose of study treatment.

The investigator must determine the primary reason for a patient's premature withdrawal from the study and must contact IRT to register the patient's treatment discontinuation within 2 days and record this information on the relevant end of phase disposition CRF page.

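### Table 6-3, Grade 3 pancreatitis: recovery beyond 28 days takes the patient off the study, while the protocol's other 28-day rules stop only alpelisib/placebo

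*Protocol*

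**What the plan says.** The Grade 3 pancreatitis row of Protocol Table 6-3 applies to patients whom the investigator judges to be deriving clinical benefit. Dosing is omitted until symptoms have fully resolved and lipase is back to Grade 1 or lower. It then resumes one dose level down. If recovery takes more than 28 days, "the patient must be discontinued from the study". The next line of the same row reads: "If toxicity reoccurs, permanently discontinue patient from alpelisib/placebo". The Grade 4 row also stops alpelisib/placebo only.

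The general rules are elsewhere:

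- Section 6.3.1.2, for an alpelisib/placebo delay of more than 28 days: "then the patient must be discontinued from alpelisib/placebo, but may continue on fulvestrant. All scheduled assessments will continue to be performed".
- Section 7.1.3: "if alpelisib dosing is held for > 28 days from the intended day then alpelisib should be permanently discontinued". The same section says that patients who stop only one of the two drugs "should NOT be considered withdrawn from the study".
- Section 6.1.2: patients who permanently stop one drug for a reason other than progression "may continue the other study drug as part of the trial therapy at the investigators discretion until disease progression".
- Table 6-3, left ventricular systolic dysfunction, if not resolved: "within 28 days permanently discontinue patient from alpelisib/placebo treatment".

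**The concern.** One event receives two incompatible instructions. A patient with Grade 3 pancreatitis that is unresolved after 28 days will normally also have been off alpelisib/placebo for more than 28 days. Under the general rules that patient may keep fulvestrant and attends every scheduled visit. Under the row, the patient leaves the study.

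The row is also out of proportion within its own block. Slow recovery from Grade 3 disease has a more complete consequence than Grade 4 disease or a recurrence, and no reason is given.

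Three things are at stake. The first is whether a patient keeps fulvestrant, the background therapy in both arms. The second is whether tumor assessments continue after a toxicity-related stop. The third is whether pancreatic monitoring continues: Section 6.3.2.1.4 requires weekly checks after treatment is stopped for pancreatic toxicity, until the event reaches Grade 1 or stabilizes. Patients still unresolved at day 28 are among those that rule is meant for.

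**Working it through.** There is no planned figure to reproduce. The check sets the rules side by side.

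| Place in the protocol | Trigger | What stops | What continues |
|---|---|---|---|
| Table 6-3, pancreatitis Grade 3 | recovery takes > 28 days | the study | nothing stated |
| Section 6.3.1.2 | alpelisib/placebo delayed > 28 days | alpelisib/placebo | fulvestrant (optional); all scheduled assessments (required) |
| Section 7.1.3 | alpelisib held > 28 days | alpelisib | the other drug, by clinical judgment; scheduled assessments; patient not counted as withdrawn |
| Section 6.1.2 | one drug permanently stopped, not for progression | that drug | the other drug (optional); scheduled safety and efficacy assessments |
| Table 6-3, left ventricular dysfunction | not resolved within 28 days | alpelisib/placebo | nothing stated |
| Table 6-3, pancreatitis Grade 3, recurrence | toxicity returns | alpelisib/placebo | nothing stated |
| Table 6-3, pancreatitis Grade 4 | Grade 4 event | alpelisib/placebo | nothing stated |

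**Do the 28-day clocks match?** Not word for word. The pancreatitis and left ventricular rows count time to recovery. Sections 6.3.1.2 and 7.1.3 count the dose hold from the intended day. Because the pancreatitis row omits dosing until recovery, the two clocks largely coincide, and a patient who meets the row will usually meet the general rule too.

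**Is the row binding?** Section 6.3.1.2 allows clinical judgment but then adds: "However, treatment must be discontinued as indicated in" Table 6-3. This makes stopping treatment mandatory. It does not by itself settle what removal from the study means.

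**What do other sections still require?** Section 4.1, Section 7.1.3 and Section 7.1.6 keep patients in tumor follow-up after treatment stops for reasons other than progression, apart from death, loss to follow-up or withdrawn consent. Section 7.1.7 continues survival follow-up whatever the reason for stopping, short of withdrawn consent or loss to follow-up. Section 6.3.2.1.4 continues pancreatic monitoring. All of these conflict with a literal reading of the row.

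**How many patients?** The Amendment 1 rationale says, in hedged terms and for the whole alpelisib program, that under 1% of treated patients may develop acute clinical pancreatitis. If 1% is assumed for this trial, purely for scale, the 572 randomized patients split 1:1 give 572 / 2 = 286 on alpelisib, and 286 × 0.01 = 2.86 cases. In the mutant cohort, 341 / 2 × 0.01 = 1.7. In the non-mutant cohort, 231 / 2 × 0.01 = 1.2. The row reaches only the part of these that is Grade 3, deriving benefit and slow to recover. The documents give no rate for that part and none for the placebo arm.

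**The case against.** The best defense is that the phrase is loose wording for stopping treatment. The repeated header of Table 6-3 limits it to dose modifications of alpelisib/placebo and lets fulvestrant continue during a hold. The glossary and Section 4.3 tie a patient's end of study to the end of study treatment. Other rows are loose as well: Grade 4 diarrhea stops treatment without naming the drug, and the QTc row interrupts study treatment as a whole.

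Much of this stands, and it makes a treatment-level reading plausible. It does not remove the conflict. Section 6.1 defines study treatment as both drugs, so even the milder reading stops fulvestrant, which Section 6.3.1.2 allows to continue.

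A reader might go further and infer that the listing of adverse events in Section 7.1.9 lets a site close follow-up for these patients. The documents do not support that. The same section says the page is completed once the patient has stopped treatment, finished safety follow-up and can no longer undergo efficacy assessment. Unresolved pancreatitis does not in itself meet the last condition.

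**Conclusion.** The wording is inconsistent and should be corrected, as a minor point. The conflict is with the instructions on fulvestrant and on scheduled assessments. Loss of follow-up is possible if a site takes the row literally, but it is not a necessary result, because several sections require follow-up to continue.

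Two stronger inferences should be avoided. One is that the row threatens the primary or key secondary analysis. SAP Section 3.8.1.1 does not censor progression-free survival for stopping treatment, survival follow-up is protected by Section 7.1.7, and only a handful of patients at most can be reached, so no material effect on either endpoint is expected. The other is that the program-wide figure of under 1% bounds the number affected here. It is a hedged statement about alpelisib across studies and says nothing about the placebo arm or about slow Grade 3 recovery. The figure of about three cases is therefore an order of magnitude resting on an assumed rate.

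The conclusion rests on the two 28-day clocks largely coinciding, which follows from dosing being omitted until recovery.

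**What to change.** In the Grade 3 pancreatitis row, replace the instruction to take the patient off the study with: *the patient must be permanently discontinued from alpelisib/placebo; fulvestrant may continue, and all scheduled assessments will continue as set out in Section 6.3.1.2*. The verbs matter: fulvestrant is optional in that section, the assessments are not.

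The cost is one phrase in one table row. Visit schedule, sample size and analysis stay as they are.

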Grade 1 (<10% body surface area (BSA) with active skin toxicity*)	
Maintain dose level
 
 Initiate topical corticosteroids 3-4 x daily, preferred compounds to use are Triamcinolone, Betamethasone as long as skin toxicity is active, during maximum 28 days 
If active rash is not resolved within 28 days of appropriate treatment, add low dose systemic corticosteroid (20-40 mg/d), such as prednisone 10 mg 3x/day.
 
For patients with symptoms like burning and/or pruritus add non-sedating anti-histamine, such as cetirizine once daily during daytime and a sedating anti-histamine such as diphenhydramine once daily at night

Grade 2 (10-30% BSA with active skin toxicity*)	
Maintain dose level.
 
 Initiate or intensify topical corticosteroids 3-4x daily, preferred compounds to use are Triamcinolone or Betamethasone as long as skin toxicity is active, up to max. 28 days Add systemic corticosteroids 20-40mg/d 
If rash resolves to ≤ G1 within 10 days systemic corticosteroid may be discontinued. For patients with symptoms like burning, stinging and/or pruritus add non-sedating anti-histamine, such as cetirizine once daily during daytime and a sedating anti-histamine such as diphenhydramine once daily at night

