Grade 3 (>30% BSA with active skin toxicity*)	
Omit alpelisib/placebo dose until rash /skin toxicity is improved to Grade 1 or resolved, recommend documentation by photography and consider performing a skin biopsy.
 
Initiate topical corticosteroids 3-4x daily, preferred compounds to use are Triamcinolone or Betamethasone for at least 28 days
 
Add systemic corticosteroids 20-40mg/d
 
If rash resolves to ≤ G1 within 10 days systemic corticosteroid may be discontinued
 
Re-start alpelisib/placebo dose once rash /skin toxicity is no longer active but fading (G1):
 
 - at a reduced dose in case of first occurrence, - If rash/skin toxicity still active in up to 10% BSA after more than 14 days, continue oral corticosteroid for at least 48 hours upon re-challenge with alpelisib/placebo; if rash and/or pruritus do not reoccur within 48 hours after re-challenge with alpelisib, systemic corticosteroid may be discontinued 
For patients with symptoms like burning, stinging and/or pruritus add a non-sedating anti-histamine such as cetirizine once daily during daytime and a sedating anti-histamine such as diphenhydramine once daily at night. Antihistamine regimen should be continued for a minimum of 28 days after re-challenge with alpelisib/placebo.

Dose Modifications for alpelisib/placebo as specified below. Fulvestrant may be continued while alpelisib/placebo dose is being held, at the investigators discretion, and as specified in Section 6.3.1	
Worst toxicity -CTCAE Grade (value)	Dose Modifications for alpelisib/placebo
Grade 4 (any % BSA associated with extensive superinfection, with IV antibiotics indicated; life-threatening consequences)	
Permanently discontinue patient from alpelisib/placebo
 
Consult a dermatologist, ensure documentation by imaging like photographs, and obtain a skin biopsy
 
Treatment may follow guidelines for Grade 3 above with the exception of rechallenge .
 
Additional measures may be taken as per local treatment guidance.
 
 •

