Any Grade of Stevens-Johnson-Syndrome /Toxic Epidermal Necrolysis/Drug Reaction with Eosinophilia and Systemic Symptoms (DRESS) or other SJS/TEN/DRESS like severe skin reactions	
Permanently discontinue patient from alpelisib/placebo
 
Consult a dermatologist, ensure documentation by imaging like photographs, and obtain a skin biopsy
 
Follow local treatment guidelines for SJS/TEN/ DRESS

**Active" skin toxicities: If there are no new lesions or new areas of involvement developing, and if lesion appearance is changing color from red to pale or light brown, it is likely the skin toxicity has begun to fade and is not to be considered "active" any longer. Treatment reduction can be considered for these areas. The appearance of skin toxicity may fade slowly, over 10 days or more but not requiring ongoing therapy.	
Immune system disorders	
Hypersensitivity	
Please see specific instructions in Section 6.3.2.1.6	
Investigations (Pulmonary disorders)	
Pneumonitis	
Please see specific instructions in Section 6.3.2.1.1 .	
Investigations (Metabolic)	
Asymptomatic amylase and/or lipase elevation (see also Section 6.3.2.1.4)	
Grade 1 (> ULN - 1.5 x ULN)	Maintain dose level
Grade 2 (> 1.5 - 2.0 x ULN)	Maintain dose level
Grade \geq 3 (> 2.0 x ULN)	
Omit dose until resolved to baseline, then
 
 • If resolved in \leq 14 days, maintain dose level • If resolved in $>$ 14 days, then \downarrow 1 dose level. 
Note:
 
 • In cases of isolated amylase elevations only, dosing may be maintained provided amylase fractionation demonstrates that pancreatic amylase is \leq Grade 1. Monitor total amylase (and continue to assess fractionated amylase) as specified in Section 6.3.2.1.4.
Note: Withhold study treatment for acute onset of new or progressive unexplained abdominal symptoms, such as severe pain or vomiting; and perform diagnostic procedures (e.g. abdominal CT scan or ultrasound) to exclude pancreatic pathology.	
Investigations (any other)	
Other adverse events	
Grade 1 or 2	Maintain dose level
Grade 3	Omit dose until resolved to \leq grade 1, then \downarrow 1 dose level
Grade 4	
Permanently discontinue from alpelisib/placebo
 
Omit dose for \geq grade 3 vomiting or grade 3 nausea only if the vomiting or nausea cannot be controlled with optimal antiemetic (as per local practice)

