Recommended therapies for skin toxicity events of all grades and as clinically indicated include:

- Mid to high potency topical steroids: triamcinolone 0.01% or fluocinonide 0.05% twice daily for at least 28 days. Recommend spray, lotion, or cream preparation for ease of application on trunk. For scalp involvement, recommend a foam or solution preparation.
- Gamma-aminobutyric acid (GABA) Agonists: Gabapentin 300mg every 8 hours, Pregabalin 50-75 mg every 8 hours (to adjust of renal impairment). Depending on patient's clinical condition be aware of potential and common side effects observed with GABA agonists such as: somnolence, dizziness (both drugs) and peripheral edema (Gabapentin) among others adverse events. For grade 4 skin events or any grade of severe cutaneous reactions (including SJS, TEN, EM, DRESS), alpelisib treatment must be permanently discontinued without any re-challenge.

Dry skin has been reported. It is recommended that patients with dry skin use mild and fragrance free soaps and detergents.

Although preclinical experiments demonstrated that patients should avoid sun exposure during treatment with ~~buparlisib~~ or alpelisib, especially when they already have experienced rash or other skin toxicities as the increased blood flow of the skin may worsen skin symptoms. Patients should be advised to take measures to protect themselves from direct exposure to sunlight, including the wearing of sunglasses as well as the regular use of sunscreen, hats, long-sleeve shirts and long pants when outdoors.

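### Protocol Table 6-3: the Grade 3 rash cell sets opposing conditions for restarting alpelisib/placebo (rash still active versus no longer active), and the severe skin reactions row leaves erythema multiforme unnamed

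*Protocol*

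**What the plan says.** Protocol Table 6-3 (Section 6.3.1.2) grades rash by BSA and by whether the toxicity is active: "Grade 1 (<10% body surface area (BSA) with active skin toxicity" and "Grade 2 (10-30% BSA with active skin toxicity". Grade 3 is active toxicity on more than 30% BSA. The table's footnote says that a rash with no new lesions or areas, and with colour turning pale or light brown, has probably begun to fade and no longer counts as active.

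The Grade 3 cell makes three statements about restart:

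- Hold: "Omit alpelisib/placebo dose until rash /skin toxicity is improved to Grade 1 or resolved".
- Restart: "Re-start alpelisib/placebo dose once rash /skin toxicity is no longer active but fading (G1".
- Sub-bullet under the restart line: "If rash/skin toxicity still active in up to 10% BSA after more than 14 days, continue oral corticosteroid", for at least 48 hours upon re-challenge.

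Section 6.3.1.2 also limits the hold. "If a patient requires a dose delay of alpelisib/placebo for > 28 days" from the intended day, alpelisib/placebo must be discontinued. Section 7.1.3 repeats the limit.

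On severe skin reactions, Section 6.3.2.1.2 requires, for "any grade of severe cutaneous reactions (including SJS, TEN, EM, DRESS), alpelisib treatment must be permanently discontinued without any re-challenge". The corresponding row of Table 6-3 names SJS, TEN and DRESS and closes with "or other SJS/TEN/DRESS like severe skin reactions". It does not name EM. The header of the table's skin section does list EM as a severe cutaneous reaction, for mandatory dermatologist consultation, and cross-refers to Section 6.3.2.1.2.

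**The concern.** A restart rule should let two sites facing the same patient reach the same decision. Here the hold line and the sub-bullet both contemplate re-exposure with limited active rash, while the restart line describes a rash that has stopped being active. With the 28-day limit, the difference is more than a few days' delay: it can separate re-exposure from permanent discontinuation. That is first a patient-safety matter. It also touches outputs that the SAP reports: reasons for discontinuation (3.6.4), adverse events leading to discontinuation (3.9.1.4) and exposure in patients who developed rash (3.6.1).

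The EM wording raises a smaller worry of the same kind. Section 6.3.1.2 directs that treatment be discontinued as Table 6-3 indicates. A site working from the table alone, and not classing low-grade EM with SJS, TEN or DRESS, could fall back on the Rash rows, where Grades 1 and 2 keep the dose unchanged.

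**Working it through.** No figure in the plan needs to be reproduced. The check sets the statements side by side.

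**Restart after Grade 3 rash**

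| Statement in Table 6-3 | State of rash it accepts | Active? |
|---|---|---|
| Hold line, with the Grade 1 definition | Below 10% BSA, or resolved | Yes, if Grade 1 |
| Restart line | Fading, labelled G1 | No |
| Sub-bullet on corticosteroid | Up to 10% BSA after more than 14 days | Yes |

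1. By definition Grade 1 rash is active. Rash active on 5% BSA is therefore Grade 1 and ends the hold.
2. The restart line requires rash that is no longer active. The same 5% rash does not meet it.
3. By the footnote, fading rash is not active; by the grade definition, Grade 1 rash is. The G1 label on the restart line therefore contradicts the table's own terms.
4. The sub-bullet sits under the restart line yet assumes re-challenge in the state that line excludes. Nothing marks it as an exception.
5. Its upper limit is 10% inclusive. Grade 1 stops below 10% and Grade 2 starts at 10%, so the sub-bullet touches the Grade 2 band at that value.

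Could a single reading save the cell? If G1 were taken to mean limited extent whether or not the rash is active, points 1 to 3 would ease. The table defines it otherwise, however, and the sub-bullet would still speak of active rash under a line that calls for inactive rash.

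**Consequence under the 28-day limit.** As an illustration with assumed days and extent, take a Grade 3 rash that improves to 5% BSA, still active, on day 10 of the hold and remains active on day 29.

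- Under the hold line, the hold ends on day 10 and the patient may be re-exposed.
- Under the restart line, the patient has not qualified by day 28. On day 29 the delay exceeds 28 days and alpelisib/placebo is permanently discontinued.

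**Erythema multiforme**

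| Place | EM named? | Instruction |
|---|---|---|
| Section 6.3.2.1.2 | Yes | Permanent stop at any grade, no re-challenge |
| Table 6-3, skin header | Yes | Mandatory dermatologist consultation; see also 6.3.2.1.2 |
| Table 6-3, severe skin reactions row | No; catch-all only | Permanent stop |

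No place says that EM may be continued or restarted. The row can be read to include EM but does not say so.

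**The case against.** Several stronger readings are tempting, and the documents do not support them.

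- **Three rival restart rules.** A reader might count three. Grade 1 active rash and rash still active on up to 10% BSA are nearly the same state, and both allow re-challenge. The 14-day text is a corticosteroid instruction and sets no restart date. The cell holds two opposing conditions. This objection narrows the point but leaves the contradiction in place.
- **A direct conflict on EM.** A reader might infer one from the missing name. The header groups EM with SJS, TEN and DRESS and sends the user to Section 6.3.2.1.2, and the catch-all can cover it. Managing EM under the Rash rows means overlooking all of these. It is an ambiguity. The Amendment 4 rationale reports 2 EM cases in 1710 exposed patients, or 2/1710 = 0.12%, so it would arise rarely. It also reports 2 SJS cases and states that a causal role of alpelisib could not be excluded for either reaction.
- **A fifth of patients affected.** Table 1-2 gives 6 Grade 3/4 rash and 11 Grade 3/4 maculopapular rash events among 84 patients, and (6 + 11)/84 = 20%. The two terms may overlap, 66 of the 84 patients took 400 mg, and at this trial's 300 mg both counts are 0 of 9. The 20% cannot be carried over.
- **An effect confined to the alpelisib arm.** The documents give no rash rates by arm for this trial, and Table 1-2 has no control arm.
- **Distorted trial results.** Amendment 5, which updated the rash guidance, is dated February 2020. Enrolment ended in July 2017, and Section 6.3.2.1.2 puts typical onset within two months of starting treatment. Few typical-onset events could fall under Amendment 5, and the documents do not show how this cell read in the protocol before it. No shift in reported exposure or discontinuation rates is demonstrated.

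**Conclusion.** The Grade 3 rash cell contradicts itself: the grade definitions and the footnote make Grade 1 active and fading rash inactive, yet the cell uses both as conditions for restart. With the 28-day limit, one patient can be re-exposed or permanently stopped according to the line read. The EM wording is a secondary ambiguity.

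The size is qualitative. The conclusion rests on the table's own definitions and on no assumed event rate. It applies to patients still on treatment under Amendment 5, and their number at risk cannot be derived from the documents. Nothing here bears on alpha or power. The primary PFS analysis uses all randomized patients (Protocol 10.1.1), and SAP 3.8.1.1 does not censor for treatment discontinuation. No view is taken on which restart or stopping rule is clinically right.

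**What to change.** 1. Reconcile the hold line, the restart line and the sub-bullet in the Rash Grade 3 cell so that one condition governs restart. State whether rash may be active and at what BSA. If the sub-bullet is meant as an exception, label it as one.
2. Use G1 throughout the cell as the table defines it, and settle the 10% boundary with Grade 2.
3. Make the EM wording identical in Section 6.3.2.1.2 and in the severe skin reactions row of Table 6-3.

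The sponsor's safety team decides which rule stands in each case. The cost is wording in two table rows and the matching section text, issued with the next amendment or by safety letter. No analysis changes.
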